Secondary Endpoints	
The secondary endpoints to be determined at the end of each treatment period (Period 1, Week 16; Period 2, Week 32; combination of treatment, Week 32) are:
 
 • IgPro20 relative bioavailability (%F) • IgPro20 PK parameters (area under the curve [AUC]_{0-tau}, AUC_{0-last}, maximum [peak] plasma drug concentration [C_{max}], minimum plasma drug concentration [C_{trough}]) • IgPro10 PK parameters (AUC_{0-tau}, AUC_{0-last}, C_{max}, C_{trough}) • The safety of IgPro10 based on: 
 ○ AEs ○ Change in other clinical tests
Study Design	Multicenter, randomized, open-label, crossover, phase 2 study
Number of Subjects	Approximately 26 eligible subjects will be enrolled and randomized to expect 20 evaluable subjects (10 subjects per treatment sequence) to complete the study.
Study Duration	
Up to 40 weeks for each subject, including a Screening Period of up to 4 weeks, a Treatment Period of 32 weeks (16 weeks each for Treatment Period 1 and Treatment Period 2) and a follow-up telephone call at 4 weeks after end of treatment
 
The overall duration of this study (eg, first subject's Screening Visit to last subject's End of Study [EOS] telephone call) will be approximately 24 months.

Study Population and Main Criteria for Eligibility	
Key inclusion criteria
 
To be enrolled into the study, subjects must meet all of the following inclusion criteria:
 
 • Age ≥ 18 years (male or female) at time of providing written informed consent • Documented diagnosis of systemic sclerosis (scleroderma) according to American College of Rheumatology and European League Against Rheumatism criteria 2013 (diffuse cutaneous form of SSc) • CCI • Disease duration ≤ 5 years defined as the time from the first non-Raynaud's phenomenon manifestation

Key exclusion criteria

Subjects must not be enrolled into the study if they meet any of the following exclusion criteria:

- Primary rheumatic autoimmune disease other than dcSSc, including but not limited to rheumatoid arthritis, systemic lupus erythematosus, mixed connective tissue disorder, polymyositis, dermatomyositis, as determined by the investigator. Note: subjects with fibromyalgia, secondary Sjogren's syndrome, and scleroderma-associated myopathy at screening are not excluded
 - CCI [REDACTED]

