2.1.2 Primary Endpoints

The primary endpoint of the study is the safety of IgPro20 based on:

Safety Endpoints	Summary Measure
AEs, including any AEs, treatment-emergent adverse events (TEAEs), serious adverse events (SAEs), and adverse events of special interest (AESIs)	
AEs measured by treatment, treatment sequence, combination of treatment, and treatment period (Period 1, Week 16; Period 2, Week 32; combination of treatment, Week 32):
 
 Number and percentage of subjects with AEs, TEAEs, SAEs, and AESIs (total, severity, causality, and outcome) Number and percentage of subjects with AEs categorized as ISRs (total, severity, causality and outcome) Rate of ISRs per subject and per infusion Onset and duration of ISRs
Change in other clinical tests	
Changes from baseline as measured by treatment, treatment sequence, combination of treatment and treatment period:
 
 Vital signs Body weight Clinical laboratory tests Electrocardiogram (ECG) Pulmonary function tests (PFTs)

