8.6 Visit Schedule

Table 2 Visit / Procedure Time Window (relative to scheduled visit / procedure)

Visit / Procedure	Time Window (Relative to Visit / Procedure)
Screening	Up to 28 days before randomization
Week 1 through Week 32	± 2 days
EOS Phone call (Week 36)	~28 days after EOT
Sequence A, Treatment Period 1 Blood collection for PK Weeks 1, 5, 9, 13, 14, and 15	Refer to the Pharmacokinetic Schedule of Assessments: Sequence A for individual sampling time windows.
Sequence A, Treatment Period 2 Blood collection for PK Weeks 17, 21, 25, 29, 30, 31 and EOT / Early Termination	Refer to the Pharmacokinetic Schedule of Assessments: Sequence A for individual sampling time windows.
Sequence B, Treatment Period 1 Blood collection for PK Weeks 1, 5, 9, 13, 14, 15, and 16	Refer to the Pharmacokinetic Schedule of Assessments: Sequence B for individual sampling time windows.
Sequence B, Treatment Period 2 Blood collection for PK Weeks 17, 21, 25, 29, 30, 31, and EOT / Early Termination	Refer to the Pharmacokinetic Schedule of Assessments: Sequence B for individual sampling time windows.
Hemolysis testing	Refer to the Schedule of Assessments .
Renal function assessments	Refer to the Schedule of Assessments .
Pregnancy testing	Before infusion
Physical examination	Before infusion
Vital signs	Before PK blood sample Before PFTs Relative to IgPro20 infusion: 
 • Within 30 min before infusion • Within 30 min after infusion Relative to IgPro10 Infusion:

	
 • Within 30 min before infusion • Within 15 minutes after initiation of infusion • Every hour during infusion • Within 15 min before increasing rate of infusion • Within 30 min after infusion
Urine and blood collection for clinical safety	Before infusion
Infusion form	After infusion of IgPro20 and IgPro10
Review Patient diary	Before IgPro20 infusion
CCI [REDACTED], CCI)	Before CCI, CCI, CCI
CCI [REDACTED]	After last infusion
CCI [REDACTED]	Before infusion
ECG ^a	Before PFTs and infusion
PFTs ^a	After vital signs and ECG and before infusion

ECG = electrocardiogram; EOS = End of Study; EOT = End of Treatment; CCI = CCI [REDACTED]; CCI = CCI [REDACTED]; min = minutes; CCI = CCI [REDACTED]; PFT = pulmonary function test; CCI = CCI [REDACTED]; PK = pharmacokinetic; CCI = CCI [REDACTED]

^a Recommended order.

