LLN	Lower limit of normal
CCI	CCI
MedDRA	Medical Dictionary for Regulatory Activities
CCI	CCI
PFT	Pulmonary function test
CCI	CCI
PID	Primary immunodeficiency
PK	Pharmacokinetics
SAE	Serious adverse event
SAF	Safety analysis set
SAP	Statistical analysis plan
SC	Subcutaneous
SD	Standard deviation
CCI	CCI
SMQ	Standardized MedDRA queries
SOC	System Organ Class
SSc	Systemic sclerosis
CCI	CCI
TEAE	Treatment-emergent adverse event
TEE	Thromboembolic event
CCI	CCI
ULN	Upper limit of normal
CCI	CCI

Glossary of Terms

Term	Definition
Baseline Value	The most recent assessment before the first infusion in Treatment Period 1.
End of Study (EOS)	The follow-up telephone call occurs 4 weeks after completing study treatment or early termination follow-up visit, whichever occurs later.
End of Treatment (EOT)	End of treatment is either end of Week 32 for completed subjects or at early termination visit.
Infusion	
IgPro10 An infusion comprises all IP exposure on one day of infusion. In the IgPro10 Treatment Periods, there are 2 to 5 consecutive days of infusions and so 2 to 5 Infusions planned per 4-week period.
 
IgPro20 An infusion comprises all IP exposure on one day (one session). In the IgPro20 Treatment Periods, there are 2 sessions and so 2 infusions planned per week.

Infusion Cycle (IgPro10 only)	One Infusion Cycle consists of 2, 3, 4 or 5 consecutive days of infusions with a planned total dose of 2 g/kg IgPro10 every 4 weeks. There are 4 planned Infusion Cycles of IgPro10 per IgPro10 Treatment Period in each Treatment Sequence.
Weekly Infusions (IgPro20 only)	A Weekly Infusion consists of 2 sessions (2 Infusions) with a planned total dose of 0.5 g/kg IgPro20 per week. There are 14 Weekly Infusions of IgPro20 per IgPro20 Treatment Period per each Treatment Sequence.
Infusion Session (IgPro20 only)	One Infusion Session consists of 1 infusion day. There are 2 Infusion Sessions within each weekly infusion with a planned total dose of 0.5 g/kg IgPro20 per week.
Protocol Deviation	
All instances when either subjects who have been entered in the study and / or the study sites deviate from the IEC / IRB-approved study protocol.
 
A key protocol deviation is any protocol deviation that could have a significant effect on the subject's safety, rights, or welfare and / or on the integrity of the study data.

Reference Visit	Reference visit for Treatment Period 1 is Week 1. Reference visit for Treatment Period 2 is Week 17.

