8.3 Study Periods Relative to Treatment

Definitions of the endpoint assessment and definition of start and end of study periods are presented in [Table 1](#) and [Table 2](#).

Table 1: Timing of Endpoint and Reference Assessments

	Definition	Start of Assessment Period	End of Assessment Period
By Treatment	1 IgPro20 Treatment Sequence A/ Treatment Period 1 and Treatment Sequence B/ Treatment Period 2	Week 1 Week 17	Week 17 ¹ Week 32
	2 IgPro10 Treatment Sequence A/ Treatment Period 2 and Treatment Sequence B/ Treatment Period 1	Week 17 Week 1	Week 32 Week 17 ²
By Treatment Sequence	1 Treatment Sequence A	Week 1	Week 32
	2 Treatment Sequence B	Week 1	Week 32
By Treatment and Treatment Period	1 IgPro20 in Treatment Period 1 Treatment Sequence A	Week 1	Week 17 ¹
	2 IgPro10 in Treatment Period 1 Treatment Sequence B	Week 1	Week 17 ²
	3 IgPro10 in Treatment Period 2 Treatment Sequence A	Week 17	Week 32
	4 IgPro20 in Treatment Period 2 Treatment Sequence B	Week 17	Week 32
Overall	1 Both Treatment Sequences, all Treatment Periods Treatment Sequence A/ Treatment Period 1, Treatment Sequence B/ Treatment Period 1, Treatment Sequence A/ Treatment Period 2, Treatment Sequence B/ Treatment Period 2	Week 1 Week 17	Week 17 Week 32

¹ Before first infusion of IgPro10.² Before first infusion of IgPro20.

Table 2: Treatment Periods

Treatment Sequence/ Treatment Period	Treatment	Start of Treatment Period	End of Treatment Period
Treatment Sequence A/ Treatment Period 1	IgPro20	Start date and time of the first IgPro20 Infusion	Start date and time of the first IgPro10 Infusion or EOS, if there is no IgPro10 Infusion
Treatment Sequence A/ Treatment Period 2	IgPro10	Start date and time of the first IgPro10 Infusion	EOS
Treatment Sequence B/ Treatment Period 1	IgPro10	Start date and time of the first IgPro10 Infusion	Start date and time of the first IgPro20 Infusion or EOS, if there is no IgPro20 Infusion
Treatment Sequence B/ Treatment Period 2	IgPro20	Start date and time of the first IgPro20 Infusion	EOS

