8.3.1 Study Periods for Adverse Events

AEs with onset date/ time at or after start of first infusion of study treatment are TEAEs. If the time of onset of an AE is missing: AEs with onset date at or after start of first infusion of study treatment are TEAEs. Assessment whether an AE is considered treatment-emergent, will take place after imputation of partially missing dates (see [Section 8.1.2](#)).

The TEAE analysis will be done for the study periods and groups shown in [Section 11](#). An AE will be counted for the analysis of a study period if the onset of the event falls within the study period. For the definition of start and end of the study periods see [Table 2](#).

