11.2 Adverse Events

All AEs will be coded by the Medical Dictionary for Regulatory Activities. System organ class (SOC), high-level group term (HLGT), high-level term (HLT), preferred term (PT), and lower-level term (LLT) will be provided in the AE dataset.

Summaries will be presented for the following combinations of Treatment Sequence and Treatment Period (respective Treatment Sequences [A/B] and Treatment Periods [1/2] are given in parentheses):

- IgPro20 (A/1 and B/2)
- IgPro10 (A/2 and B/1)
- IgPro20/ Treatment Period 1 (A/1)
- IgPro20/ Treatment Period 2 (B/2)
- IgPro10/ Treatment Period 1 (B/1)
- IgPro10/ Treatment Period 2 (A/2)
- Total (A/1, A/2, B/1, and B/2)

Infusion site reactions (ISR) comprise all AEs reported within the MedDRA HLTs “Administration site reactions NEC” or “Infusion site reactions”.

Summaries of AEs created to assess the COVID-19 impact are described in Section 7.4.

Refer to Section 11.3 for the definition of Adverse Events of Special Interest (AESIs).

- An overview summary of TEAEs, including number of subjects, percentages of subjects, and the number of events by Treatment Sequence, treatment, and Treatment Period including the following:
 - Any TEAE
 - Any serious TEAE
 - TEAEs leading to interruption of IP
 - TEAEs leading to permanent discontinuation of IP
 - TEAEs leading to withdrawal from study
 - Temporally associated TEAEs
 - Treatment-emergent AESIs (Hemolysis, TEE, Acute Renal Injury)
 - Any serious treatment-emergent AESIs
 - Treatment-emergent AESIs leading to permanent discontinuation of IP
 - Treatment-emergent AESIs leading to withdrawal from study

- Related treatment-emergent AESIs
 - Treatment-emergent AESIs by Grade
 - Treatment-emergent AESIs Grade 3 and above
 - TEAEs by causality (related to IP)
 - TEAEs by severity (mild, moderate, severe)
 - TEAEs by outcome (“recovered or resolved” vs. all other outcomes combined)
 - Any ISR
 - ISRs leading to interruption of IP
 - ISRs leading to permanent discontinuation of IP
 - ISRs leading to withdrawal from study
 - ISRs by causality (related to IP)
 - ISRs by severity (mild, moderate, severe)
 - ISRs by outcome (“recovered or resolved” vs. all other outcomes combined)
- The following descriptive tables will be generated for TEAEs, including number of subjects, percentages of subjects, and the number of events:
 - TEAEs by SOC and PT
 - TEAEs by PT
 - TEAEs by SOC, PT, and maximum severity (without number of events)

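### SAP Table 2 counts Period 2 adverse events to Week 36 but closes Period 1 at crossover, so the split-period AE columns compare about 19-20 weeks with 16

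*SAP*

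**What the plan says.** - **Counting rule.** SAP 8.3.1: "An AE will be counted for the analysis of a study period if the onset of the event falls within the study period". It refers to SAP Table 2 for the start and end of each period.
- **Period ends (SAP 8.3, Table 2).** In Sequence A, Period 1 ends at "Start date and time of the first IgPro10 Infusion or EOS, if there is no IgPro10 Infusion". Sequence B has the mirror rule with IgPro20. Period 2 ends at EOS in both sequences.
- **Protocol time frame.** Protocol 2.1.2 sets the primary AE summary at "Period 1, Week 16; Period 2, Week 32; combination of treatment, Week 32". SAP Table 1, which times the endpoint and reference assessments, also ends Period 2 at Week 32.
- **When EOS falls.** The protocol synopsis plans two 16-week periods and "a follow-up telephone call at 4 weeks after end of treatment". The visit-window table in Protocol 8.6 puts the EOS call at Week 36, about "28 days after EOT". The SAP glossary adds: "End of treatment is either end of Week 32 for completed subjects or at early termination visit". However, Protocol 3.1, SAP 4.1 and the study-design figure footnotes place follow-up about four weeks after the last dose, which is earlier.
- **What is tabulated.** SAP 11.2: "Summaries will be presented for the following combinations of Treatment Sequence and Treatment Period". The list has the pooled IgPro20 and IgPro10 columns, the four split cells (A/1, B/2, B/1, A/2) and a total. The measures are numbers of subjects, percentages and event counts. Apart from the ISR rate per infusion there is no exposure denominator.
- **Declared changes.** SAP 5 lists departures from the protocol. The move from Week 32 to EOS for AE counting is not among them.

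**The concern.** Adverse events are the primary endpoint, and SAP 11.2 prints the same product in Period 1 and Period 2 as separate columns. A reader will compare A/1 with B/2 and B/1 with A/2 to see whether a product's safety depends on when it is given, and will compare the two products within a sequence. In each of these contrasts one side has about three to four more weeks in which an event can be counted. Those weeks fall after dosing has stopped, so they describe follow-up more than treatment. The percentages also answer a different question from the Week 32 endpoint in Protocol 2.1.2, and nothing in SAP 5 tells the reader so.

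**Working it through.** **1. Locate EOS by reproducing the plan's own duration.** Screening 4 + Period 1 16 + Period 2 16 + follow-up 4 = 40 weeks. This matches the stated maximum of 40 weeks and puts EOS at Week 36.

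**2. Period lengths for a subject who crosses over.** Nominal day = (week − 1) × 7 + 1, so Week 17 is Day 113 and Week 36 is Day 246.
- Period 1: Days 1 to 112 = 112 days = 16.0 weeks.
- Period 2 by nominal visit day: 246 − 113 = 133 days = 19.0 weeks.
- Period 2 if EOS is 28 days after the end of Week 32 (Day 224): 224 + 28 − 112 = 140 days = 20.0 weeks.
- Excess over Period 1: 3 to 4 weeks, or 3/16 = 19% to 4/16 = 25%.

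**3. Time from last dose to close of period.** Take the last IgPro20 session on Day 4 of Week 14 or 30, and the last IgPro10 infusion on Day 5 of a five-day cycle in Week 13 or 29.
- Period 1: about 2.6 weeks (IgPro20) and 3.4 weeks (IgPro10).
- Period 2: about 5.6-6.6 weeks and 6.4-7.4 weeks.

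**4. Effect on a subject percentage.** The documents give no AE hazard, so this step rests on assumption. Let p be the 16-week incidence, e the extra weeks (3 or 4) and f the hazard in the extra weeks relative to the first 16. Then the Period 2 incidence is 1 − (1 − p)^((16 + f·e)/16).

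| 16-week incidence | f = 0.5 | f = 1 (constant hazard) |
|---|---|---|
| 10% | 10.9-11.2% | 11.8-12.3% |
| 30% | 32.3-33.1% | 34.5-36.0% |
| 50% | 53.1-54.1% | 56.1-58.0% |

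Event counts scale by (16 + f·e)/16. That is 17.5/16 = 1.09 to 18/16 = 1.13 at f = 0.5, and 19/16 = 1.19 to 20/16 = 1.25 at f = 1.

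A split cell holds about 20/2 = 10 evaluable to 26/2 = 13 randomized subjects. At 50% incidence the excess is 0.031 × 10 = 0.3 to 0.080 × 13 = 1.0 subject.

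**5. Which columns are affected.** With n subjects per sequence, pooled IgPro20 (A/1 + B/2) has 16n + (19 to 20)n subject-weeks, and pooled IgPro10 (B/1 + A/2) has the same. Both average 17.5 to 18 weeks, so the tail largely cancels between products while the sequences stay balanced. It does not cancel in A/1 versus B/2, in B/1 versus A/2, or between products within one sequence.

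**6. Sensitivity to the other EOS statement.** Place EOS 28 days after the last dose.
- IgPro10, last cycle starting on Day 197 (first day of Week 29): 197 + 28 − 113 = 112 days = 16.0 weeks. If the cycle ends on Day 201, it is 116 days = 16.6 weeks.
- IgPro20, last session on Day 207: 207 + 28 − 113 = 122 days = 17.4 weeks.

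The excess falls to 0-1.4 weeks. Even with a constant hazard, 50% becomes at most 1 − 0.5^(17.4/16) = 53%.

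**The case against.** The case for leaving the plan alone has several parts, and much of it stands.

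- **Counting to EOS has protocol support.** Protocol 9.4 observes AEs to four weeks after the last visit, and Protocol 10.3.2.1 defines treatment-emergent events with a start but no end. This stands. Collecting and reporting late events is right, and the tension lies partly inside the protocol. It does not give the split columns a common length or explain the departure from Week 32.
- **SAP Table 1 serves visit-based assessments and Table 2 serves AEs.** This is also fair: the two tables need not match. The difference from Protocol 2.1.2 remains.
- **The main product columns are protected.** This stands (step 5). The ISR rate per infusion and TEAEs with onset within 72 hours of an infusion are also little affected, because the added weeks contain no infusions.
- **The constant-hazard figures are too high.** The extra weeks are off drug, and after EOT the only scheduled contact is one telephone call without laboratory tests or examination. They should be read as the upper range.
- **Period 1 does not always close at Week 17.** For subjects who never cross over it runs to EOS.

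Two stronger readings are tempting and are not supported. One is that the windows must make Period 2 look worse for both products. Protocol 4.3.1 withdraws subjects who stop treatment, so Period 2 holds only those who got through Period 1, and that selection can pull the other way. The other is that the trial depends on these columns to detect carry-over. Protocol 3.3.1 gives that task to IgG trough samples, and SAP 7.3 states that no hypothesis is tested.

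**Conclusion.** The point holds for the split-period columns and for product contrasts within a sequence. For subjects who cross over, and with EOS at Week 36, Period 2 is observed for about 19-20 weeks against 16. It runs four weeks past the protocol's Week 32 time frame, and SAP 5 does not say so.

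The size is modest: at a 16-week incidence of 50%, about 3-4 percentage points with half the hazard off drug, up to 6-8 points with a constant hazard, and at most about one subject per cell. It is smaller still if EOS is four weeks after the last dose. Week 36 is the better-supported reading, since the schedule, the visit-window table and the 40-week total agree on it.

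A reader might infer that the AE tables as a whole are not comparable. The documents do not support that, because the pooled by-product columns carry nearly equal follow-up.

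**What to change.** **Preferred.** In SAP 11.2, add events per subject-week at risk next to each percentage in the by-period columns, with time at risk taken as the time each subject spends in the Table 2 period. This also handles early terminations and subjects who do not cross over.

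One caution: if the off-drug hazard is lower, the Period 2 rate is diluted. At half the hazard it is 17.5/19 = 0.92 to 18/20 = 0.90 of the Period 1 rate. The rate should therefore stand beside the percentage and not replace it.

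**Alternative, for the split-period columns only.** End Period 2 at the end of Week 32. The nominal Week 32 visit day would leave only 15 weeks. Show later events in a separate follow-up column and keep them in the pooled by-product and total columns. Leave Period 1 ending at the first infusion of the next product. A fixed 112-day cap on every column would trim pooled columns that are already balanced, and could leave events before a delayed crossover in no product column.

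**In either case.** Declare the Week 32 versus EOS choice in SAP 5, and reconcile the statements on EOS timing in Protocol 3.1, SAP 4.1, the study-design figure footnotes and the visit-window table.

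**Cost.** SAP wording and one extra rate or column. No new data are needed, and no event drops out of the report.

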8.3.2 Study Periods for Concomitant Medications

Concomitant Medication start and end dates will be assigned to study periods as described below.

- Start relative to treatment
 - Assign to 'BEFORE' if the concomitant medication start date/time is prior to study treatment start date/time; if subject has not taken any study treatment; or the concomitant medication start date/time is missing and the concomitant medication end date/time is before the study treatment start date/time.
 - Assign to 'DURING PERIOD 1' if the concomitant medication start date/time falls into Treatment Period 1 ([Table 2](#)); or the concomitant medication start date/time is missing.
 - Assign to 'DURING PERIOD 2' if the concomitant medication start date/time falls into Treatment Period 2 ([Table 2](#)).
 - Assign to 'AFTER' if the concomitant medication start date/time is after the date/time of the end of the last treatment period.
- End relative to treatment
 - Assign to 'BEFORE' if the concomitant medication end date/time is prior to study treatment start date/time or if the subject has not taken any study treatment.
 - Assign to 'DURING PERIOD 1' if the concomitant medication end date/time falls into Treatment Period 1 ([Table 2](#)).
 - Assign to 'DURING PERIOD 2' if the concomitant medication end date/time falls into Treatment Period 2 ([Table 2](#)).
 - Assign to 'AFTER' if the concomitant medication end date/time is after the date/time of the end of the last treatment period; or the concomitant medication end date/time is missing.

If a start or end date/time is partially missing, the imputation takes place before the classification of the medication in the categories above.

8.3.3 Study Periods for Medical History

Prior medical conditions are those which end before the start of first infusion of IP. All other Medical History entries are Concomitant medical conditions, including those with missing end date. Assessment whether a Medical History is considered prior or concomitant, will take place after imputation of partially missing end dates (see [Section 8.1.2](#)).

